### **5.2.1 Administrative, behavioural, and regulatory procedures**

- Informed consent for screening
- Assignment of a screening number
- Collection of the following:
  - Demographic information
  - Locator information
- Eligibility assessment
- HIV pre- / post-test counselling and HIV/STI risk reduction counselling
- Provision of HIV prevention methods (e.g. condoms)
- Provide reimbursement
- Schedule next visit

### **5.2.2 Clinical procedures**

- Medical history
- Targeted physical examination
- Pelvic examination (if needed)
- Provision of test results

### **5.2.3 Laboratory procedures**

- HIV rapid testing
- Urine pregnancy testing

## **5.3 Enrolment visit (day/month 0)**

The enrolment visit will only be commenced for participants who are found to be eligible. Written informed consent for study participation will be obtained before any enrolment (or “on-study”) procedures are conducted.

### **5.3.1 Administrative, behavioural, and regulatory procedures**

- Review eligibility
- Informed consent for enrolment and stored specimens
- Assignment of a participant identification (PID) number
- Update locator information
- HIV pre- / post-test counselling and HIV/STI risk reduction counselling
- Contraceptive counselling
- Provision of HIV prevention methods (e.g. condoms)
- Collect HIV risk perception and baseline behavioural data
- Assess acceptability of HIV prevention options
- Provide reimbursement
- Schedule next visit

### **5.3.2 Clinical procedures**

- Medical history
- Targeted physical examination
- Pelvic examination
- Genital specimen collection
- Blood draw
- Provision of test results

### **5.3.3 Laboratory procedures**

- HIV rapid testing
- Urine pregnancy testing
- Collection of dry blood spots
- CD3/CD4/CD8 count
- STI testing (Urine, Plasma and/or genital specimen)
- Serum and plasma archive
- Genital specimen archive

## **5.4 Follow-up visits**

Monthly follow-up visits are scheduled on a 28-day schedule for the first three months, with a 14-day visit window on either side. Thereafter visits will be scheduled on an 84-day schedule (every three months), with a 28-day visit window on either side. For participants who do not complete scheduled visits within the allowable window, the visit will be considered “missed” and relevant CRFs will be completed to document the missed visit.

HIV-uninfected study participants who become infected during follow-up will be referred to one of the long-term CAPRISA Acute Infection cohort studies, which have provisions for care, ART and support for those infected with HIV. These services are provided at no cost to the participant. For those who do not wish to continue in any of these studies post-seroconversion, participants will be referred to their preferred AIDS care provider which could include government or non-governmental AIDS care services for ongoing clinical management and care.

Participants who become pregnant during follow-up may be maintained in this study, however follow-up procedures may be modified according to guidelines specified in the study-SOPs, i.e. the principal change will be the discontinuation of pelvic examinations and genital specimen collection after 24 weeks of pregnancy.

### **5.4.1 Administrative, behavioural, and regulatory procedures**

- Update locator information
- HIV pre- / post-test counselling and HIV/STI risk reduction counselling
- Contraceptive counselling
- Provision of HIV prevention methods (e.g. condoms)
- Collect HIV risk perception and behavioural data
- Provide reimbursement
- Schedule next visit

### **5.4.2 Clinical procedures**

- Medical history
- Targeted physical examination
- Blood draw (at quarterly follow-up visits only or if indicated, e.g. at the time of suspected HIV seroconversion)
- Provision of test results
- Pelvic examination (at quarterly follow-up visits only or if indicated, e.g. at the time of suspected HIV seroconversion)
- Genital specimen collection (at quarterly follow-up visits only or if indicated, e.g. at the time of suspected HIV seroconversion)

### **5.4.3 Laboratory procedures**

- HIV rapid testing
- Urine pregnancy testing
- Collection of dry blood spots
- HIV confirmatory tests – RNA PCR, CD3/CD4/CD8 counts, Western Blot and/or ELISA (only if indicated)
- STI testing (only if indicated)
- Serum and plasma archive (at quarterly follow-up visits only or if indicated, e.g. at the time of suspected HIV seroconversion)
- Genital specimen archive (at quarterly follow-up visits only or if indicated, e.g. at the time of suspected HIV seroconversion)

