### **3.2 Secondary objectives**

- To measure the acceptability of, uptake and adherence to the range of behavioural and biomedical prevention options, including pre-exposure prophylaxis (when available).
- To measure HIV and other sexually transmitted infection incidence rates.
- To assess trends in sexual behaviour.
- To measure pregnancy rates.

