### **5.5.2 Clinical procedures**

- Medical history
- Targeted physical examination
- Blood draw
- Provision of test results
- Pelvic examination (at quarterly follow-up visits only or if indicated, e.g. at the time of suspected HIV seroconversion)
- Genital specimen collection (at quarterly follow-up visits only or if indicated, e.g. at the time of suspected HIV seroconversion)

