## **5.6 Interim contacts and visits**

Interim visits may be performed at any time during the study, for a number of reasons, which include, but may not be limited to, the following:

- For administrative reasons, e.g., a participant may have questions for study staff or may need to re-schedule a follow-up visit.
- For interim STI counselling and or treatment in response to STI symptoms.
- For interim HIV counselling and testing in response to presumed exposure to HIV or seroconversion symptoms.
- Contraception counselling and/or provision
- To provide participants with the results of confirmatory HIV test results, per algorithm in Appendix III.
- For other reasons – at the request of study staff or the participant.

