#### **6.2.2 Secondary analysis**

Acceptability of HIV prevention options will be measured using acceptability questionnaires administered during interviews with the participants. These interviews will include questions about the uptake of different prevention options. Prevention choices will be described by giving the number and percentage of participants who prefer various prevention options at different time points. The acceptability and uptake of the HIV prevention options will be summarised at different time points. The acceptability and uptake in different age groups will be compared using Fisher's exact test.

Adherence to prevention options will be measured as appropriate according to the prevention method; for example oral tablets will be measured using pill counts and drug level data. Adherence will be summarised at various time points, by giving the percentage adherence. For pill counts adherence will be calculated as the number of pills taken according to pill count (number dispensed minus number returned) divided by the number of pills prescribed in the time period. Adherence for other options may be defined as a binary variable: adherent, not adherent – based on some predefined criteria. The proportion adherent participants will then be summarised at various time points.

STIs will be measured using laboratory assessments of urine, plasma and/or genital specimens. The incidence rate of the various STIs (including HIV) will be calculated as the number of new infections over the time on study. A Poisson distribution will be assumed for the confidence intervals of incidence rates.

Sexual behaviour will be ascertained through interviews with the enrolled participants where questions about sexual behaviour related to HIV risk (e.g. number of partners, condom use and use of HIV prevention interventions, etc.) will be asked. Trends in sexual behaviour will be summarised over time using means and proportions at the various time points. If needed longitudinal mixed models will be fit to determine whether there are changes over time.

Pregnancy will be defined as a positive pregnancy test. The pregnancy incidence rate will be calculated as the number of new infections over the time on study. A Poisson distribution will be assumed for the confidence intervals of incidence rates.

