## Appendix I: Schedule of evaluations

Procedure	Screen	Enrol	Follow-up		Exit
	Screening (up to 30 days)	Enrolment (day/month 0)	Monthly follow-up (months 1 & 2)	Quarterly follow- up (month 3 onwards a )	Study exit visit
	V0	V1	V2, V3	V4 - V22	V23
Administrative, Behavioural and Regulatory Procedures					
Informed consent for screening	X				
Obtain screening number	X				
Eligibility assessment	X	X			
Demographic information	X				
Informed consent for enrolment		X			
Informed consent for specimen storage		X			
PID assignment		X			
Locator information	X	X	X	X	X
HIV pre- / post-test counselling and risk reduction counselling	X	X	X	X	X
Contraception provision and counselling		X	X	X	X
Provision of HIV prevention methods	X	X	X	X	X
HIV risk perception and behavioural assessment		X	X	X	X
Assessment of acceptability of HIV prevention options		X			X
Provide reimbursement	X	X	X	X	X
Schedule next visit	X	X	X	X	
Clinical Procedures					
Medical history, including targeted physical examination	X	X	X	X	X
Pelvic examination		X	0	X	X
Genital specimen collection		X	0	X	X
Phlebotomy		X	0	X	X
Provide test results	X	X	X	X	X
Perform Laboratory Evaluations					
HIV serology (rapid tests)	X	X	X	X	X
Urine pregnancy test	X	X	X	X	X
Dry blood spots		X	X	X	X
HIV RNA PCR, Western blot and/or ELISA b		0	0	0	0
CD3 / CD4 / CD8 count b		X	0	0	0
Plasma and serum archive b,c		X	0	X	X
STI testing (Urine, Plasma and/or genital specimen) b		X	0	0	X
Genital specimen for archive c		X	0	X	X
Amount of blood collected c in mls:	0	75 (90)	0 (20)	50 (70)	80 (100)
Footnotes: a This quarterly visit schedule will continue until participants are exited from this study.					
b Blood volumes: HIV confirmatory tests (PCR, WB and/or ELISA) (15ml); CD3, CD4, CD8 (5ml); Storage (50ml); STI testing (10ml).					
c The stored serum, plasma and genital specimens will be used for potential post-study assessments for markers of safety, risk exposure, PrEP adherence and resistance. In addition, stored plasma will be used for retrospective RNA PCR testing to confirm whether incident cases of early HIV infection during the study occurred post-enrolment.					
( ) = includes additional bloods for suspected seroconverters (i.e. HIV confirmatory tests and CD3/CD4/CD8 counts).					
0 = if indicated					

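### The STI incidence rate in Section 6.2.2 divides by all time on study, but STI tests are routine only at enrolment and exit, so for transient STIs it is too low and falls as follow-up lengthens

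*Protocol*

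**What the plan says.** Section 3.2 lists among the secondary objectives "To measure HIV and other sexually transmitted infection incidence rates". Section 6.2.2 fixes the ascertainment, "STIs will be measured using laboratory assessments of urine, plasma and/or genital specimens", and the estimator: "The incidence rate of the various STIs (including HIV) will be calculated as the number of new infections over the time on study". Confidence intervals assume a Poisson distribution.

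Section 5.4.3 gives the follow-up procedure as "STI testing (only if indicated"). In Appendix I the row "STI testing (Urine, Plasma and/or genital specimen") carries an X at enrolment and at exit and a 0 in both follow-up columns, where "0 = if indicated". The protocol does not define when an STI test is indicated. Section 5.6 names one STI-related reason for an interim visit: "For interim STI counselling and or treatment in response to STI symptoms". Sections 4.3.2.1 and 7.4 describe STI care as syndromic.

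For the exit visit, Section 5.5.2 has "Genital specimen collection (at quarterly follow-up visits only or if indicated"), whereas Section 5.5.3 and Appendix I list genital specimens and STI testing at exit without that restriction.

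**The concern.** Dividing events by all time on study gives an incidence rate only if new infections can be detected throughout that time. Here, infections that prompt no test can be found only at the exit visit, which may be up to 5 years after enrolment. Those that clear before exit drop out of the numerator while the whole follow-up stays in the denominator.

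The result mixes a rate of prompted diagnoses with a point prevalence at exit spread over the follow-up time. It would vary with how long women stay in this open cohort, so it could not be compared across sites, calendar periods or other cohorts. The Poisson interval would convey sampling error around a quantity that is not the incidence named in the objective.

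**Working it through.** **1. Is this the actual schedule or a slip in one place?**

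| Appendix I row | Enrolment | Months 1-2 | Quarterly (V4-V22) | Exit |
|---|---|---|---|---|
| HIV rapid tests | X | X | X | X |
| Genital specimen for archive | X | 0 | X | X |
| STI testing | X | 0 | 0 | X |

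Sections 5.3.3, 5.4.3 and 5.5.3 match the STI row, so it is the plan. V4 to V22 is 22 - 4 + 1 = 19 quarterly visits, the last at month 3 x (22 - 3) = 57, none with a routine STI test. HIV is tested at every visit and is not affected.

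**2. Inputs.** The protocol gives no STI rate, precision or power, so there is no figure to reproduce. From the protocol: follow-up of up to 5 years (Section 3.3) and a retention target of 90% a year (Section 4.5). Assumed, not in the documents:
- a true rate R of about 20 per 100 person-years;
- a share s of 10-50% of infections that prompt a test and are counted at once;
- a mean untreated duration D of 0.5-1.5 years for the rest;
- all women uninfected after the enrolment test;
- every woman reaching exit at time T.

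**3. Formulas.** Unprompted infections arise at rate λ = (1 - s)R and clear at rate 1/D. Write k = λ + 1/D.
- Prevalence at exit: p(T) = (λ/k)(1 - exp(-kT)).
- Expected unprompted infections by T: N(T) = λ{T - (λ/k)[T - (1 - exp(-kT))/k]}.
- Share of unprompted infections detected: p(T)/N(T), close to (D/T)(1 - exp(-T/D)).
- Planned estimate: sR + p(T)/T. True rate: sR + N(T)/T.

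**4. One case in full: s = 0.2, D = 1, T = 5.** λ = 0.16 and k = 1.16.
- p(5) = 0.1379 x (1 - exp(-5.8)) = 0.1375. The estimate is 0.04 + 0.1375/5 = 0.0675, or 6.8 per 100 person-years.
- N(5) = 0.16 x {5 - 0.1379 x [5 - 0.8595]} = 0.7086. The true rate is 0.04 + 0.7086/5 = 0.1817, or 18.2 per 100 person-years.
- The ratio is 0.37.

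The same case gives 13.5 per 100 person-years (ratio 0.71) with exit at 1 year and 10.2 (ratio 0.55) at 2 years. True incidence is essentially unchanged while the estimate halves.

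**5. Share of unprompted infections detected (λ = 0.20; within 0.02 of these values for λ from 0.05 to 0.30).**

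| Mean duration | Exit at 1 y | 2 y | 5 y |
|---|---|---|---|
| 0.5 y | 43% | 24% | 10% |
| 1 y | 63% | 42% | 19% |
| 1.5 y | 72% | 54% | 28% |
| lifelong | 100% | 100% | 100% |

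**6. Ratio of estimated to true rate over s = 10-50% and D = 0.5-1.5 y:** 0.49-0.87 with exit at 1 year, 0.32-0.78 at 2 years and 0.20-0.66 at 5 years.

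**7. Loss before exit.** At the retention target, 0.9^5 = 0.59 of women remain at year 5. A woman lost earlier has no scheduled STI test after enrolment, so only prompted infections can be counted for her, while her time stays in the denominator. Step 6 assumes that everyone reaches exit and is optimistic in this respect.

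**8. With scheduled tests.** Setting T to the interval between tests, and assuming women are uninfected after each test, quarterly testing detects 79%, 88% and 92% of unprompted infections for D = 0.5, 1 and 1.5 years. The ratio is then 0.81-0.96. With yearly testing it is the 1-year range in step 6. In both cases the ratio no longer depends on total follow-up.

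**The case against.** Testing on indication is a legitimate choice in an observational cohort, and this is a descriptive secondary rate with no hypothesis test, precision target or power claim. The protocol does not say which STIs are tested, and plasma is among the listed specimens, so some may be persistent. Those would still be found at exit. Procedures are also guided by SOPs, and pelvic examinations are scheduled quarterly, so signs as well as symptoms could prompt a test. All of this stands and limits the size of the problem. It does not remove the mismatch, because the protocol itself fixes the all-time denominator, and no analysis plan can recover infections that were never tested for.

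Four stronger readings are tempting but not supported:
- **Most asymptomatic infections are missed.** This depends on duration and follow-up. With 1 year of follow-up and a 1-year duration, about 37% are missed; with lifelong infection, none.
- **Detection depends on symptoms alone.** This is an inference from Sections 4.3.2.1, 5.6 and 7.4, because the indication is undefined. In the working, s can stand for any prompt.
- **Hazard ratios in the primary HIV model are inflated, because seroconverters have an early exit visit and hence an early STI test.** Section 6.2.1 adjusts for baseline variables and adds only behavioural variables as time-dependent covariates, so no post-baseline STI covariate is planned. The exit test also follows two sets of confirmatory tests (Section 7.6 is silent on this; Section 7.5.2 sets it out), so it comes after the estimated infection date.
- **The exit STI test may not take place at all.** The restriction in Section 5.5.2 concerns pelvic examination and genital specimens. Blood is drawn at exit without restriction, and urine or plasma may be used for STI testing.

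**Conclusion.** The point holds for STIs other than HIV that can clear without being tested for. Sections 5.4.3 and Appendix I agree on the schedule, and Section 6.2.2 applies an estimator that does not fit it. The resulting rate is biased low, and more so the longer women are followed.

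The direction follows from the documents. The size does not: the range of 0.20-0.66 at 5 years rests on the assumed share prompting a test and the assumed durations, and it is milder for shorter follow-up. Since the cohort runs for up to 5 years, the 5-year figures describe the longest follow-up and not the typical woman. The primary analysis is not affected. The exit-visit wording in Section 5.5.2 is a separate, minor contradiction.

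**What to change.** 1. In Section 6.2.2, report the rate of STIs diagnosed on indication and, separately, STI prevalence at enrolment and at exit. Do not call the pooled figure an incidence rate, and align the wording of the objective in Section 3.2. This costs wording only.
2. If the incidence objective is to be kept, commit in the protocol to STI testing of quarterly specimens at fixed visits, and use only time between scheduled tests as the denominator. Time after a woman's last scheduled test then drops out. The cost is the assays. Three limits apply: residual specimens of women who refuse long-term storage are destroyed at study end once protocol-required testing is complete (Section 8.4), so this testing would have to be protocol-required; genital collection stops after 24 weeks of pregnancy (Section 5.4); and the documents do not show that the archived specimens suit diagnostic assays.
3. Reconcile Section 5.5.2 with Section 5.5.3 and Appendix I on pelvic examination and genital specimens at exit. This is wording only.

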## **5.5 Study Exit Visit**

### **5.5.1 Administrative, behavioural, and regulatory procedures**

- Update locator information
- HIV pre- / post-test counselling and HIV/STI risk reduction counselling
- Contraceptive counselling
- Provision of HIV prevention methods (e.g. condoms)
- Collect HIV risk perception and behavioural data
- Assess acceptability of HIV prevention options
- Provide reimbursement

### **5.5.2 Clinical procedures**

- Medical history
- Targeted physical examination
- Blood draw
- Provision of test results
- Pelvic examination (at quarterly follow-up visits only or if indicated, e.g. at the time of suspected HIV seroconversion)
- Genital specimen collection (at quarterly follow-up visits only or if indicated, e.g. at the time of suspected HIV seroconversion)

### **5.5.3 Laboratory procedures**

- HIV rapid testing
- Urine pregnancy testing
- Collection of dry blood spots
- STI testing
- Serum and plasma archive
- Genital specimen archive
- HIV confirmatory tests – RNA PCR, CD3/CD4/CD8 counts, Western Blot and/or ELISA (only if indicated)

## **5.6 Interim contacts and visits**

Interim visits may be performed at any time during the study, for a number of reasons, which include, but may not be limited to, the following:

- For administrative reasons, e.g., a participant may have questions for study staff or may need to re-schedule a follow-up visit.
- For interim STI counselling and or treatment in response to STI symptoms.
- For interim HIV counselling and testing in response to presumed exposure to HIV or seroconversion symptoms.
- Contraception counselling and/or provision
- To provide participants with the results of confirmatory HIV test results, per algorithm in Appendix III.
- For other reasons – at the request of study staff or the participant.

## **6 STATISTICAL CONSIDERATIONS**

### **6.1 Sample size**

A sample size of 2,500, allowing for 10% loss to follow-up, will be large enough to identify known and new risk factors of HIV infection. Multivariate models will be fitted with numerous co-variables to determine which risk factors are associated with HIV infection. This sample size will also allow sufficient power within subgroups (i.e. women who prefer various prevention options and women in various age groups) and will enable us to compare risk factors between various groups.

### **6.2 Data analysis**

#### **6.2.1 Primary analysis**

To assess the risk factors for HIV infection proportional hazards regression models will be used to estimate the hazard rate ratio, along with a 95% confidence interval, controlling for the selected baseline prognostic variables. Behavioural variables measured over time after baseline will be included in the analysis as time-dependent covariates.

Date of HIV infection will be estimated as the midpoint between the last negative HIV test date and the first confirmed positive HIV test date. Participants who do not become HIV infected before their last study visit will be censored on the day of their last negative HIV test. Time to HIV infection, in days, will be computed as the difference between the estimated date of HIV infection, and the enrolment date, plus one. Time to censoring will be computed as the difference between the date of censoring and the enrolment date, plus one.

#### **6.2.2 Secondary analysis**

Acceptability of HIV prevention options will be measured using acceptability questionnaires administered during interviews with the participants. These interviews will include questions about the uptake of different prevention options. Prevention choices will be described by giving the number and percentage of participants who prefer various prevention options at different time points. The acceptability and uptake of the HIV prevention options will be summarised at different time points. The acceptability and uptake in different age groups will be compared using Fisher's exact test.

Adherence to prevention options will be measured as appropriate according to the prevention method; for example oral tablets will be measured using pill counts and drug level data. Adherence will be summarised at various time points, by giving the percentage adherence. For pill counts adherence will be calculated as the number of pills taken according to pill count (number dispensed minus number returned) divided by the number of pills prescribed in the time period. Adherence for other options may be defined as a binary variable: adherent, not adherent – based on some predefined criteria. The proportion adherent participants will then be summarised at various time points.

STIs will be measured using laboratory assessments of urine, plasma and/or genital specimens. The incidence rate of the various STIs (including HIV) will be calculated as the number of new infections over the time on study. A Poisson distribution will be assumed for the confidence intervals of incidence rates.

Sexual behaviour will be ascertained through interviews with the enrolled participants where questions about sexual behaviour related to HIV risk (e.g. number of partners, condom use and use of HIV prevention interventions, etc.) will be asked. Trends in sexual behaviour will be summarised over time using means and proportions at the various time points. If needed longitudinal mixed models will be fit to determine whether there are changes over time.

Pregnancy will be defined as a positive pregnancy test. The pregnancy incidence rate will be calculated as the number of new infections over the time on study. A Poisson distribution will be assumed for the confidence intervals of incidence rates.

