### **3.3 Study overview**

This is a prospective observational cohort study.

Up to 2,500 sexually active, HIV-uninfected women between the ages of 18 and 30 years will be enrolled from an urban, a peri-urban and a rural site in KwaZulu-Natal, South Africa. Potential study participants will be screened for eligibility and eligible participants will be enrolled in the study within 30 days of screening. Participants will have monthly visits for the first three months post-enrollment, thereafter visits will be scheduled every three months.

HIV and pregnancy testing will be performed at each study visit and the incidence of pregnancy, as well as HIV and other STIs will be assessed. HIV/STI risk reduction messages and HIV prevention methods (e.g. condoms) will be offered to all participants using consistent prevention messages. It is anticipated that PrEP use will increase during this study. Uptake and adherence to PrEP and other HIV prevention modalities will be assessed during follow up. A HIV risk perception and behavioural assessment using an interviewer administered questionnaire will be conducted at each visit. In addition, an acceptability assessment of expanded HIV prevention options (oral tablets, rings, injectables and implants) will be conducted through an interviewer administered questionnaire at enrolment and study exit. Blood and genital specimens will be collected and stored every three months and will be used for potential post-study assessments for markers of safety, risk exposure, PrEP adherence and resistance. In addition, stored plasma will be used for retrospective RNA PCR testing to confirm whether incident cases of early HIV infection during the study occurred post-enrolment.

An open cohort will be maintained for up to 5 years. Participants may be simultaneously enrolled in or may transition to other studies as appropriate.

Overviews of the study visit and procedures schedules are presented in Appendix I: Schedule of Evaluations.

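### Section 6.2.2 sets a plain Poisson interval for STI incidence without saying whether repeat episodes count; if they do, the interval can be too narrow, and if they do not, the stated denominator is too large

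*Protocol*

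**What the plan says.** Section 6.2.2 gives one formula for all infections: "The incidence rate of the various STIs (including HIV) will be calculated as the number of new infections over the time on study". The interval follows: "A Poisson distribution will be assumed for the confidence intervals of incidence rates". The numerator is not limited to a woman's first infection, the denominator does not stop at an event, and no allowance for several events in one woman is mentioned.

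The pregnancy paragraph uses the same formula, apparently carried over: "The pregnancy incidence rate will be calculated as the number of new infections over the time on study". Its event definition is "Pregnancy will be defined as a positive pregnancy test", and the Poisson sentence is repeated.

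The design leaves room for repeat events. Section 3.3 says "An open cohort will be maintained for up to 5 years". Section 7.4 provides free syndromic STI treatment, and Section 5.6 foresees interim visits for STI symptoms. Section 5.4 adds: "Participants who become pregnant during follow-up may be maintained in this study". HIV is different: it happens once, and under Section 7.5.2 a woman with two sets of positive confirmatory tests is scheduled for study exit.

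On detection, Section 5.4.3 makes testing at follow-up visits conditional ("STI testing (only if indicated"). Appendix I schedules it routinely only at enrolment and exit.

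**The concern.** A Poisson interval for a rate takes the variance of the event count to equal its mean. Repeat events do not break this by themselves. It fails when some women have persistently higher risk than others, because their episodes then cluster and the total count varies more than Poisson. A cohort set up to find risk factors, drawn from three different sites and including STI clinic clients (Section 4.3.1), presupposes such differences.

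HIV and STI incidence and pregnancy rates are secondary objectives (Section 3.2), and these intervals are the only inference that Section 6.2.2 specifies for the rates. What is at stake is whether an interval labelled 95% has that coverage or, on the first-episode reading, whether the rate itself is right.

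**Working it through.** **Plan's own figure.** There is none to reproduce. The protocol states no STI or pregnancy rate, event count or interval width. Section 6.1 gives only "A sample size of 2,500, allowing for 10% loss to follow-up", with no event rate.

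**Inputs.** From the protocol: 2,500 women and up to 5 years. Assumed, because the protocol does not give them: an episode rate r per woman-year for one STI, follow-up T years, and a gamma frailty variance v for differences in risk between women. Mean episodes per woman are m = r × T.

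**Reading 1: all episodes counted.**
- Variance/mean of the total count: φ = 1 + v × m.
- Poisson width as a share of the correct width: 1/√φ.
- Coverage of the nominal 95% interval: 2Φ(1.96/√φ) − 1.

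| r | T | m | v | φ | Width share | Coverage, formula | Coverage, simulated |
|---|---|---|---|---|---|---|---|
| 0.10 | 2.5 | 0.25 | 0 | 1.00 | 100% | 95.0% | 95.4% |
| 0.05 | 1 | 0.05 | 0.5 | 1.025 | 99% | 94.7% | not run |
| 0.10 | 2.5 | 0.25 | 1 | 1.25 | 89% | 92.0% | 92.8% |
| 0.20 | 2.5 | 0.50 | 1 | 1.50 | 82% | 89.0% | 89.0% |
| 0.20 | 5 | 1.00 | 1 | 2.00 | 71% | 83.4% | 83.8% |
| 0.20 | 5 | 1.00 | 2 | 3.00 | 58% | 74.2% | 74.3% |

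Worked line: v = 1 and m = 1 give φ = 2; 1.96/√2 = 1.386; 2Φ(1.386) − 1 = 0.834. The first row shows that repeats with equal risk leave the Poisson interval intact.

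The simulations used 2,500 women and 3,000 runs, so the simulation error near 95% is √(0.95 × 0.05/3,000) = 0.4 percentage points. In the same five simulated settings, intervals with variance clustered on the woman covered 95.1% to 95.4%.

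**Reading 2: first episodes only.** With a constant rate and equal risk, the expected number of first episodes per woman is 1 − exp(−rT). Dividing by all time on study gives (1 − exp(−rT))/T, which is a fraction (1 − exp(−rT))/(rT) of the true rate.
- r = 0.1, T = 2.5: (1 − exp(−0.25))/0.25 = 0.885, about 12% too low.
- r = 0.2, T = 5: (1 − exp(−1))/1 = 0.632, about 37% too low.

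If person-time instead ends at the first episode, the Poisson interval had simulated coverage of 93.5% to 94.7% in the same settings, which is close to nominal.

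**Pregnancy.** A pregnant woman cannot conceive again for some months. With an assumed 0.75-year non-susceptible period, 5 years of follow-up and equal risk, the simulated variance/mean was 0.85 at 0.08 per woman-year and 0.80 at 0.15 (1,500 runs). The Poisson interval is then too wide by a factor 1/√0.85 = 1.08 to 1/√0.80 = 1.12. Differences in risk between women would push the other way.

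**The case against.** The strongest reply is that the protocol never says repeat episodes count. With first-episode counting and person-time ending at the event, the Poisson interval is adequate for any STI and for pregnancy, not only for HIV. The counting rule and variance estimator for a descriptive rate are also commonly left to the SAP, which is not at hand. This stands in part: nobody can say from the protocol that the intervals are too narrow, only that they will be if repeats count and risk differs. But Section 6.2.2 is not silent. It fixes numerator, denominator and interval, and its denominator does not fit first-episode counting. Section 6.2.1 shows that the authors do write event and censoring rules for HIV; there are none here.

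A second reply is that repeats may be few. Testing in follow-up is only if indicated, STIs are measured by laboratory assessment, and the phrase about the various STIs reads most naturally as one rate per STI. Then only repeats of the same STI matter, and two different STIs in one woman do not. Five years is also a maximum, in a cohort from which women may move to other studies. This stands, and it is why the lower end of the effect is negligible.

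Two stronger inferences are tempting, but the documents do not support them. A reader might carry the narrow-interval claim over to pregnancy; the non-susceptible period pulls that interval the other way. A reader might also say that differences by site, age or period will look too certain; Section 6.2.2 plans no such comparison of STI or pregnancy rates. Its only age-group comparison concerns acceptability and uptake.

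**Conclusion.** The point holds conditionally and is minor. As written, the STI formula is sound on neither reading: counting all episodes makes the Poisson interval too narrow whenever risk varies between women, and counting first episodes over all time on study makes the rate too low. HIV is not affected by the repeat-event problem.

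The size cannot be read from the protocol. Under the assumed rates and gamma frailty, all-episode coverage lies between about 95% and 74%, with 83% at one episode per woman and frailty variance 1. On the first-episode reading, the rate is about 12% to 37% too low for the two rates shown. With few detected repeats and short follow-up, both effects are small. No primary result or decision rule depends on these intervals.

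**What to change.** State the counting rule in Section 6.2.2 and match the interval to it:
- **HIV:** keep an exact Poisson interval.
- **Each other STI:** either (a) count the first episode, end person-time at that event and use a Poisson interval, or (b) count all episodes and use a variance clustered on the woman, through a Poisson model with a log person-time offset and robust standard errors, or a negative binomial model.
- **Pregnancy:** make the same choice, and replace the word for infections in that formula with pregnancies.

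The cost is a sentence or two and a software option, with no new data. The downside is that STI intervals may widen under (b).
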